5.2 DATA SECURITY

All applicable statutory requirements and mandatory codes of practice in respect of confidentiality (including, where applicable, medical confidentiality) in relation to such research subjects or their legal guardians.

Data Management Plans will be provided to the TM and documented in the TMF, detailing relevant security information about the data system. System access will be strictly restricted through user-specific passwords to the authorised research team members. It is a legal requirement that passwords are not shared, and that only those authorised to access the system are allowed to do so. If new staff members join the study, a user-specific username and password must be requested and a request for access to be revoked must be requested when staff members leave the project.

Participant intials, date of birth and ethnicity will be entered into the Medrio EDC system. No more identifiable data will be entered into the Medrio EDC system. Trial sites will maintain a master participant log linking participant identifiers to Participant Identification Numbers (PINs).

Only participant email address and site can be entered in the EDC before participant has signed a consent form to participate in the trial (as this triggers the eConsent process). No further data will be entered in the EDC unless consent is signed by the participant and authorised staff member. The Medrio eConsent does not form part of the exported dataset for the study.

A link back document for participant information including contact details (study PIN, full name, NHS number, address, email, telephone) will be uploaded to the KCL CREATE Trusted Research Environment (TRE) by the Research Associates attached to each NHS Gender Clinic, for the purposes of contacting participants for follow up data if unresponsive to Medrio ePRO automated data requests. No identifiable data will be held outside theTRE.

5.3 DATA QUALITY PROCESSES

At the database design stage, validations will be programmed into the systems to minimise data entry errors by querying the data entered in real time with sites. The CI team will undertake

appropriate reviews of the entered data, in consultation with the project analyst, where appropriate for the purpose of data cleaning and will request amendments to the Medrio EDC system data as required.

Site staff will respond to Data Clarification Requests (DCRs) within the EDC as required. No data will be amended independently of the study site responsible for entering the data. The KCTU will provide the study team with a Data Management Plan for Medrio EDC which will be filed in the Trial Master File (TMF).

5.4 DATABASE LOCK

At the end of the trial, the site PI's will review all the data for each participant in the Medrio EDC system and provide electronic sign-off to verify that all the data are complete and correct. The TM will confirm all checks are complete and all data queries have been resolved prior to database lock. At this point, with the agreement of the Senior Statistician, all data can be formally locked for analysis.

When the final data extract is requested, KCTU staff will remove all data entry user access prior to data extract and will retain only 'monitor' access for site PI's and other relevant individuals. Upon request following completion of statistical analyses, KCTU will provide a copy of the final exported raw dataset to the CI in .csv format and the CI will onward distribute to sites as appropriate. Once sites have received copies of their individual datasets and confirmation of receipt has been received, the TM will request that all user access is removed from the Medrio EDC system. A copy of the final dataset, analysis dataset and code will be stored in the TMF at the end of the study.

5.5 Data Monitoring

Data collected by this study will be taken to a Data Monitoring Committee (DMC). As this is not a trial, the data shall only be given to the committee for further information on their whole overview of the PATHWAYS programme rather than for the committee to give recommendations based on the data accrued, as would be in a randomised controlled trial.

Data taken to the committee will consist of AEs, Serious AEs (SAEs) and outcome data by timepoint, as it accrues. Adverse events and serious adverse events are collected differently and less comprehensively in this study as opposed to how they would be in an RCT. This will be made clear in the reports to the DMC.

To begin with, data from this study will be taken to the DMC on a yearly basis. This is due to follow-ups being at yearly intervals for participants. This timeline may be altered at the discretion of the DMC if they feel they need to see the data more often.

6. ADVERSE EVENT MANAGEMENT AND REPORTING

Adverse events (AEs) will be recorded based on specific items endorsed by either the CYP or parent/ caregiver in the questionnaires as outlined in section 4.5.1 and the PATHWAYS HORIZON distress protocol, including the ASQ, Annual Health Update and RCADS-25.

Any SAEs occurring to research participants will be reported to the main REC (the REC that gave favourable opinion of the study) within 15 days of the Chief Investigator becoming aware of the event, or the Deputy Chief Investigator in the Chief Investigator's absence.

The up to date SAE report form for non-CTIMPs available from the HRA website will be used for this indication.

Based on the data that are being collected AEs will include:

- 1. Depression or anxiety scores with a T score ≥80 on annual questionnaires when they previously were not (RCADS)
- 2. Suicidal thoughts and behaviours (ASQ)
- 3. Unplanned A&E attendances for mental health (Annual Health Update)
- 4. Unplanned hospital admission for any reason other than mental health (Annual Health Update)

SAEs will be recorded when:

1. Unplanned hospital admission for mental health (Annual Health Update)

Standard safeguarding procedures will be followed if a CYP or parent endorses the questionnaire item relating to an unplanned hospital admission for mental health (SAE). All PATHWAYS researchers who have access to the research database or direct contact with research participants will have level 3 safeguarding training. The PATHWAYS research team also consists of two senior clinical academics with longstanding experience of managing safeguarding concerns, who will be available daily to advise on any safeguarding concerns.

7. ETHICS APPROVAL

Prior to the start of the study, a favourable opinion will be sought from a Research Ethics Committee (REC) for the study protocol, PIS, informed consent form and related documents. The CI will be responsible for preparing the submission packs for REC and Health Research Authority (HRA) approval.

Individual participants will consent to participate. The trial will be conducted in compliance with the Declaration of Helsinki (1996) ³⁴, the principles of Good Clinical Practice (GCP) and in accordance with all applicable regulatory requirements.

The CI is responsible for submitting an end of study declaration to the REC, defined as completion of all data collection. The CI will submit a final report to the REC and study sponsors with the results, including any publications/abstracts, at the conclusion of the trial within the timelines defined in the regulations. In the event the study is ended prematurely, the CI will notify the REC, citing the reasons for the premature termination.

7.1 PROTOCOL AMENDMENTS AND VERSION CONTROL OF STUDY DOCUMENTS

The TM will be responsible for preparing and submitting protocol amendments to the REC. Participant facing documents (e.g. PIS, consent form) will be prepared by the co-ordinating centre (KCTU) and the co-ordinating centre is responsible for maintaining version control. All correspondence, including submission packs with attachments and approvals, will be filed in the TMF. Recruiting study sites are responsible for communicating relevant approved information to participants.

The TM will be responsible for updating the ISRCTN registry following relevant protocol amendments.

7.2 **POTENTIAL RISK OR HARM TO STUDY PARTICIPANTS**

The PATHWAYS-HORIZON study has identified potential risks and burdens for participants and has implemented measures to minimise them. The study aims to balance these risks with the potential benefits, ensuring that participants' well-being is prioritised throughout the research process.

Participants may experience emotional distress when discussing sensitive topics related to gender incongruence, mental health, and personal experiences. All participants will be given information about voluntary sector organisations offering urgent mental health advice and they will be informed they can pause or stop the study at any time. Participants will also be asked whether they would like a researcher to contact them to discuss their participation should they feel distressed or want further support. Researchers will be trained to handle sensitive topics with care and empathy.

Participation in the study will require time and effort, including completing questionnaires and attending interviews, which could be seen as intrusive or inconvenient. The study will aim to minimise intrusion by aligning research sessions with routine clinic assessments and integrating research activities into participants' existing routines as much as possible. Flexible scheduling and the option to complete assessments online or via telephone will be provided to accommodate participants' preferences and reduce inconvenience. Participants will be given ample notice of appointments and assessments, and efforts will be made to minimise disruption to their daily lives.

As is the case for any study, there is a small potential risk of breach of confidentiality, which could lead to unintended disclosure of personal information. All participant data will be pseudonymised and separated from identifying information after data collection. Unique identification codes will be used and access to personal data will be restricted to authorised members of the research and clinical teams. Strict data protection protocols will be followed to ensure confidentiality, and a data safe haven (see section 5.2) will be used to store participant contact details.

Participants, especially those with limited English proficiency, may misunderstand the study's purpose, procedures, or their rights. Information will be provided in clear, accessible language, and interpreters will be available as needed. Researchers will ensure that participants fully understand the study before obtaining assent/consent.

7.2.1 Assessment and management of risk

Responses to questionnaire items that indicate safeguarding risk will be routinely monitored and standard safeguarding procedures will be followed. The CYP's clinician at the CYPGS will be informed should a participant disclose that they have experienced significant distress requiring a hospital admission. If they are no longer open to the CYPGS, then their GP may be informed, as appropriate.

It is explained clearly in the information sheet that should the research team have concerns about a CYP's safety or wellbeing, the research team may discuss this with the CYP's clinical team in the CYPGS or their GP.

Any issues raised that reach the threshold of needing to contact the young person/ parent will be discussed with one of the clinical investigators, all of whom have up to date safeguarding level 3 training. The study team have a clear protocol for recording concerns.

8. STATISTICAL METHODS

8.1 **PRIMARY OUTCOME**

The primary outcome for the PATHWAYS-HORIZON study is the mental health status and wellbeing of children referred to national gender services for young people in the UK. This will be measured using the CYP self-report version of the KIDSCREEN-10 ²³ questionnaire, which evaluates quality of life across ten dimensions.

8.2 **SECONDARY OUTCOMES**

Secondary outcomes can be split into smaller subcategories. All outcomes are marked as to whether they are continuous, binary, time-to-event or will only be displayed descriptively. Scales of gender-related distress, mental health symptoms and physical health measures:

- Utrecht Gender Dysphoria Scale Gender Spectrum (UGDS-GS), continuous
- Revised Children's Anxiety and Depression Scale (RCADS), continuous
- Body Image Scale Gender Spectrum (BIS-GS), continuous
- Parental Attitudes of Gender Expansiveness Scale for Youth (PAGES), continuous
- SCOFF questionnaire, binary
- Sexual attraction questionnaire, descriptive only
- Adolescent Primary Care Traumatic Stress Screen (APCTSS), continuous
- Romantic Relations questionnaire, descriptive only
- Gender identity question, descriptive only
- Height (cm) and weight (kg) as BMI, descriptive only
- Physical health diagnoses, descriptive only
- Parental 'about yourself' questionnaire, descriptive only

Scales of suicidal ideation, hospitalizations, mood symptoms, behavioural and functional difficulties, quality of life ratings

- Ask Suicide-screening Questions (ASQ) for suicidal ideation and behaviour, binary
- Child Behaviour Checklist (CBCL), continuous
- Youth Self-Report (YSR) for behavioural and emotional problems, continuous
- KIDSCREEN-52 for quality of life, all 10 domains continuous
- Difficulties in Emotion Regulation Scale 18 (DERS-18), for young people, DERS-29 for parents, continuous
- Hospitalisations of participants, binary
- Social transition questionnaire, descriptive only

Experiences of therapeutic options

- Rates of referral to, uptake of and completion of:
- Psychological therapy, binary
- Occupational therapy, binary
- Speech and language therapy, binary
- Clinical nursing, binary
- Youth work support, binary
- School/College support, binary
- Non-endocrine pharmacological treatments, binary

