2.1.2 Secondary Objectives

- 1. To improve understanding of how care options are experienced by CYP and their parents/carers/legal guardians.
- 2. To develop a novel interview-based outcome measure that focuses on CYP's aspirations and goals from gender care.
- 3. To explore similarities and differences in the holistic perspectives of CYP and their parents/carers/legal guardians to gain a comprehensive understanding of how gender incongruence affects CYP.

3. Participants & Recruitment.

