4.1.3 Annual follow-up visits

Follow up data will be collected as per the Schedule of Events in Table 1 above for the relevant yearly visit and ongoing section. At each follow up timepoint, a status form is completed in the study database to indicate whether the participant remains in the CYPGS.

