4.4.3 Annual follow-up timepoints only

4.4.3.1 Annual health update

A questionnaire was designed to assess the CYP's current height and weight, current prescribed medications and diagnoses including neurodevelopmental, mental health and physical health, received in the past year. The questionnaire also assesses the number of GP appointments, planned surgeries or procedures, A&E attendances, or other unplanned admissions in the past year. The reasons for the GP appointments and A&E attendances will be elicited. The length of hospital admission for planned surgeries or procedures and admissions following an A&E attendance will also be measured. At follow-up, parents/carers/legal guardians of CYP under 16 will be sent this questionnaire and asked to complete it with their CYP. Self-report questionnaires will only be obtained from young people aged 16 and above. Duration: 6 minutes.

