5. DATA MANAGEMENT

5.1 DATA MANAGEMENT

The Medrio EDC system dataset, which includes data from the Medrio ePRO module, forms the dataset for the study. The CI will act as custodian for the trial data.

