8.4.2.2 BINARY OUTCOMES

For binary outcomes, a similar method as used in the primary outcome analysis will be used. A mixed-effects logistic regression will be used in place of the mixed linear model.

The fixed effects and random effects will be the same as those used in the primary analysis.

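### Twenty of the 21 referral, uptake and completion rates that protocol section 8.2 lists as secondary outcomes have no data item in any scheduled form

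*Protocol*

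**What the plan says.** Section 8.2, under its heading on experiences of therapeutic options, promises the "Rates of referral to, uptake of and completion of" seven care options. Each is marked binary, ending with "Non-endocrine pharmacological treatments, binary". For binary outcomes section 8.4.2.2 states that "A mixed-effects logistic regression will be used in place of the mixed linear model", with the primary model's fixed and random effects. Under section 8.4.1 those include timepoint, so the plan expects these outcomes to be observed repeatedly.

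On collection, section 4.1.3 says "Follow up data will be collected as per the Schedule of Events in Table 1 above". Section 5.1 adds that "The Medrio EDC system dataset, which includes data from the Medrio ePRO module, forms the dataset for the study".

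Two follow-up forms could plausibly carry care data:

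- **Annual Health Update (section 4.4.3.1).** It covers height, weight, current prescriptions and diagnoses. On service use, "The questionnaire also assesses the number of GP appointments, planned surgeries or procedures", together with A&E attendances and unplanned admissions.
- **Status form.** Section 4.1.3 says that "a status form is completed in the study database to indicate whether the participant remains in the CYPGS". Section 4.4.3.2 says that it documents status in the study.

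**The concern.** An outcome needs a place where it is recorded. Section 8.2 names seven care options at three stages, but the schedule of events contains no form about therapies or interventions. Medical history is taken once, at baseline. Section 1.2 describes the clinical assessment as leading to a formulation and then to an agreed intervention plan, so uptake and completion of that plan unfold over the period that the follow-up forms would have to cover.

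If the protocol is followed as written, a named family of secondary outcomes would reach database lock almost empty. The study would then say little about what non-medical care participants were offered and received, although the introduction itself notes that such care has not been rigorously evaluated. Dates of referral, start and completion may also be hard to reconstruct later, because section 3.1 keeps participants in follow-up after discharge and after transfer to adult services.

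**Working it through.** The point rests on no power or sample-size figure, and the protocol gives no number to reproduce. The check sets each stated rate against each scheduled form.

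**Step 1: count the outcomes.** Section 8.2 gives 7 options and 3 stages: 7 × 3 = 21 rates.

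**Step 2: look for a data item.** The sources are Table 1, Annex 2 (Tables 2 to 5) and the form descriptions in sections 4.1.3, 4.3 and 4.4.

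| Form | When | Content as described | Rates supplied |
|---|---|---|---|
| Registration, eligibility, consent, demographics | Baseline | Identification, referral to and first appointment at the gender service itself, consent, background | 0 |
| Medical history (4.4.1.1) | Baseline | Ten domains; none named as therapy referral, uptake or completion | 0 |
| SNAP-IV, SCQ, parental questionnaire | Baseline | ADHD symptoms, autism traits, parent's gender identity and sex | 0 |
| Status form (4.1.3, 4.4.3.2) | Each follow-up | Whether still in the service; status in the study | 0 |
| Annual Health Update (4.4.3.1) | Each follow-up | Height, weight, current prescriptions, diagnoses, GP visits, procedures, A&E, admissions | 1, in part |
| Quality-of-life, mental-health, gender, relationship and parental-attitude questionnaires | Baseline and each follow-up | Scale scores and categorical responses | 0 |
| Withdrawal form | Ongoing | Withdrawal or death | 0 |

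**Step 3: tally by option.**

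- Psychological therapy, occupational therapy, speech and language therapy, clinical nursing, youth work and school/college support: 6 × 3 = 18 rates, none with a source.
- Non-endocrine medication: referral and completion have no source (2 rates). Uptake has a partial source (1 rate).
- Without a source: 18 + 2 = 20 of 21. With a partial source: 1 of 21.

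The medication source is partial because it is an annual snapshot of current prescriptions. No matching baseline item is named, and a course begun and ended between two assessments could be missed.

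**Step 4: look for a source outside the forms.**

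- *Clinical-record extraction.* Section 4.4.1.1 describes transcription from the electronic record or a source data worksheet into the study database, but only for the baseline medical history.
- *Consent to use routine records.* Section 3.3 lists this only for the novel outcome measure study, which section 4.8 sizes at 75 dyads. Against about 3600 in the cohort, that is 75 / 3600 = 2.1%.
- *Linkage.* Section 2 makes linkage to health and educational databases optional, in the context of longer-term follow-up. It is not named as a source for these outcomes.

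**The case against.** The strongest reply is that the protocol describes its forms without reproducing them. The two descriptions of the status form are short and are not field lists, so a therapy item could exist unmentioned. The services record assessments in a consistent way, a route from clinical record to study database already exists at baseline, and linkage consent is sought. A reader might infer from the schedule that these outcomes can never be analysed. The documents do not support that: they show that no source is scheduled or named, not that none could be found. The gap itself stands, because sections 4.1.3 and 5.1 tie follow-up data to the schedule and to the EDC dataset, and none of these routes is assigned to these outcomes.

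Three other readings also go too far:

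- **That all seven outcomes lack any source.** The prescription item partly serves medication uptake, so the count is six outcomes plus two of the three stages of the seventh.
- **That a secondary objective fails.** Secondary objective 1 is "To improve understanding of how care options are experienced by CYP and their parents/carers/legal guardians". The protocol does not map the section 8.2 rates to it, and counts of referral or completion do not measure experience.
- **That baseline medical history comes before most referrals.** The protocol gives no referral timing. Section 3.4 allows baseline up to five months after the first appointment, and later joining; section 3.1 invites participants already discharged. For some, baseline may follow referral. A single baseline form still cannot supply annual follow-up data.

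It is also fair to say that these are secondary outcomes in an observational cohort. Therapy receipt is neither a fixed effect in section 8.4.1 nor a subgroup in section 8.6, so the primary analysis and the scale-based secondary outcomes are untouched.

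**Conclusion.** The concern holds as a mismatch between the outcome list and the data schedule. Six of the seven care-option outcomes, and the referral and completion parts of the seventh, have no data item in any form the protocol schedules or describes: 20 of 21 rates. The remaining rate, medication uptake, has only a partial source. As scheduled, the 20 could not be computed from the dataset defined in section 5.1, and the repeated-measures logistic model in section 8.4.2.2 would have nothing to fit for them. An analysis plan can define how to analyse data but cannot create data that no form collects.

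This rests on two assumptions: that the form descriptions in sections 4.1.3 and 4.4 fairly reflect the forms' content, and that no unlisted form is in use. The main-cohort consent form is not available here, so nothing is concluded about whether it would permit use of clinical records.

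**What to change.** Choose one of three routes and make sections 4.4, 5.1 and 8.2, Table 1 and Annex 2 agree.

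1. **Collect it.** Add to the annual follow-up forms (status form or Annual Health Update) a short item for each of the seven options: referred, started, completed since the last assessment. Provide a version that works for discharged participants, and list it in Table 1 and Annex 2.
2. **Extract it.** Name a clinical-record extraction at each annual timepoint, and confirm that main-cohort consent covers it. State how care is captured for participants who have left the service.
3. **Drop or narrow it.** Remove these outcomes from section 8.2, or restrict them to what is collected. At present that is medication uptake, as current prescriptions at annual follow-up.

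The cost of the first route is one short form section and a small added time. The protocol gives no figure. If one assumes 1 to 2 minutes per participant per year, a full annual round of 3600 would take 3600 × 1 / 60 = 60 hours to 3600 × 2 / 60 = 120 hours in total. For comparison, Table 1 allows 1 minute for the status form and 6 for the Annual Health Update. The second route adds record-search time and a check of consent wording. The third costs no data collection but gives up the description of non-endocrine care.
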